- Week 1: up to 15 min on the Monday (minimum 10 min), up to 25 min on Wednesday and up to 30 min on Friday (days of the week can change to adjust to subject schedule)

Pre-screening and Visit Description

[figure not shown]

Figure 2 - Schematic representation of the intervention. Subjects will be assigned to either: Aerobic or anaerobic exercise (AE or nAE – grey squares) and active or sham transcranial direct current stimulation (tDCS - black squares).

Pre-screening Procedures

During the pre-screening process, the subject will contact a co-investigator usually via a phone call. During this call, the co-investigator will discuss in greater depth the details of the study, explain the study procedures and encourage the subject to ask questions. The co-investigator will ask the subject questions from the phone screening questionnaire, or if the subject desires, this can be arranged to be done in the privacy of the laboratory. We will follow partner's institutional policies regarding communication with study subjects including use of encryption.

Once this information is collected, the co-investigator will consult with the PI regarding the eligibility of the subject, who will then give approval for the subject to come to our laboratory for the screening procedure.

Visit 0 – Consent and Screening Visit

At screening visit the PI and/or a co-investigator will conduct once more a review of inclusion/exclusion criteria to determine the subject's eligibility for enrollment. Study procedures will be reviewed with the subject, and documentation of informed consent will be obtained.

At Screening, the following procedures will be completed:

- Discuss study-specific procedures with the subject
- Obtain a signed and dated consent form
- Review inclusion and exclusion criteria
- Pregnancy test (if applicable)
- Conduct a Demographics Survey, including self-reported hand dominance
- Conduct a Recruitment Survey

Visit 1 – Pre-training walking

If the subject passes the screening for exercise (see section IV) as reviewed by PI, subject will undergo the pre-training walking (30' treadmill at baseline HR). If he/she complete the pre-training walking successfully as described above, then he/she will be randomized during visit 1.1. (subjects will also complete the adverse effects for aerobic exercise questionnaire)

- Pregnancy test (if applicable and wasn't done in visit 0 in the case of eConsent)

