**Visits 0 and 1 may be completed in the same day or broken up into two separate visits as the subject prefers*

Daily pain reports will be collected for the two weeks between V1 and V2.

VISITS 1.1 – 1.3: Subjects will be randomized during visit 1.1. The two groups will participate in a different conditioning exercise program for two weeks according to their group assignment (see section VI). At visits 1.1, we will conduct assessments of pain, quality of life, TPSP, CPM, TMS and EEG acquisition (we will offer the possibility of splitting this visit into two visits if the subject gets too tired). At visit 1.3, we will conduct assessments of pain and quality of life, TPSP and CPM. In all these visits we will conduct AE adverse effects questionnaires.

VISITS 2, 11, 17: assessments of pain (except visit 2), quality of life (except visit 2), TSPS, CPM, TMS and EEG acquisition. At the same visit, tDCS and AE will be performed. Also, tDCS and AE adverse effects questionnaire.

VISITS 6 and 14: tDCS, AE, tDCS and AE adverse effects questionnaire, CPM, TSPS, assessments of Pain

[figure not shown]
VISITS 3, 5, 8, 10: tDCS only and tDCS adverse effect questionnaire. The subjects will have the option of choosing to do the visits remotely home-based tDCS (Soterix Medical 1X1 tDCS mini-CT stimulator device), in order to decrease the burn of daily visits at our site.

[figure not shown]
VISITS: 4, 7, 9, 12, 13, 15, 16: tDCS, AE and tDCS and AE adverse effects questionnaire.

VISIT: 18: Pain and quality of life assessments, TMS, EEG, CPM, TSPS.

[figure not shown]
Replacement of missed sessions (though all the effort will be made to avoid missing sessions) will be allowed to up to 20% of missed sessions (up to 4 total visits) according to the treatment schedule. Follow-up and assessments will be encouraged even if more than 20% of missed sessions given data will be analyzed as ITT (though we expect this to be low). We will allow the following visit windows:

- *between visit 1 and 1.1: 2 weeks*
- *between visits during the conditioning period (from visit 1.1 to 1.3): 2 weekdays*
- *between visit 1.3 and visit 2: up to 1 week*
- *between visit 17 and visit 18: up to 2 weeks (before or after the final follow-up, meaning visit 18 could happen 2.5 months to 3.5 months from visit 17)*
- *between Visit 2 and Visit 17: up to 6 weeks*

[figure not shown]

Detailed Protocol 16

Detailed Protocol 17

VII. DESCRIPTION OF ASSESSMENTS

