TSPS Protocol – Heat pulses will be generated by a TSA-II Stimulator (Medoc Advanced Medical Systems, Ramat Yishai, Israel) delivered to the right dominant proximal volar forearm using an appropriate size embedded HP-thermode. We will follow the adapted protocol suggested by [43], in which the HP-thermode was programmed to deliver pulses rising/fall of 1-2-s, depending on subject's heat-evoked pain threshold, from adapting temperatures to peak temperatures, with a plateau of .7-s. Subjects will be trained to determine the temperature necessary to elicit pain-60 (see CPM protocol below) . Subsequently, they will receive 1 train of 15 repetitive heat stimuli at 0.4 Hz to the same area, in which by being suitable for eliciting TSPS in most subjects, allows the rating of individual pain stimuli and is unlikely to induce peripheral sensitization [44]. . TSPS will be calculated as the difference between heat pain rating after the 15th stimulus minus the 1st stimulus.

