CPM Protocol – The protocol involves two conditions, the *test-stimulus* and the *conditioned-stimulus*. We will follow the adapted protocol suggested by Granot, 2008 [84] and Nir, 2011[85]. We will first determine the pain-60 test temperature (which is the temperature that induces pain experience at a magnitude of 60 on a 60-100 NPS) by applying a Peltier thermode (Medoc Advanced Medical Systems, Ramat Yishai, Israel) on the right forearm of subjects and delivering three short heat stimuli (43, 44, and 45 °C), each lasting for 7 s starting from the time the stimulus intensity reaches the destination temperature. Subjects will be asked to rate the level of pain intensity using a numerical pain scale (NPS) ranging from 0 = “no pain” to 100 = “the worst pain imaginable”. If the first temperature of 43 °C is considered too painful (>60), we will stop the series and will provide additional stimuli at lower temperatures of 41 and 42 °C. If the three temperatures of (43, 44, and 45 °C), were not able to achieve pain-60, we will deliver additional stimuli at 46, 47, and 48 °C until the desired pain level of 60 (in the unlikely event that neither of those temperatures were sufficient to elicit pain-60, we will consider it to be 48°C). Once determined the pain-60 temperature, we will administer the test stimulus, applied for 30 s at that temperature and subjects will be asked to rate their levels of pain intensity 3 times: at 10, 20 and 30s after the thermode reaches the pain-60 temperature (mean scores of the the three pain rating will be calculated). Five minutes after delivering the test stimulus, for the *conditioned-stimulus*, the left hand of the subject will be immersed in a bath of water set at 10 to 12°C for 30 seconds. Then, the same pain-60 temperature will be applied on the right forearm of the subject (left hand will still be immersed), for 30 s and subject will again be asked to rate their levels of pain intensity 3 times after the thermode reaches the pain-60 temperature: at 10, 20 and 30s (mean scores of the three pain rating will be calculated). CPM response will be calculated as the difference between the average of pain ratings from the test stimulus minus the average of pain ratings during the conditioned stimulus.

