Physical performance: running speed, HR range and distance that have been ran for the 30 minutes of exercise will be collected during exercise.

tDCS Adverse Effects Questionnaire: At the end of each stimulation session, subjects will complete a 5-point scale questionnaire that evaluates potential common adverse effects of tDCS (headache, neck pain, scalp pain, scalp burning sensation, tingling, skin redness, sleepiness, concentration, and acute mood change).

Exercise Adverse Effects: During each AE session, subjects will be monitored (HR variability). The session will be stopped if the HR is superior to 80% of HRmax [36], or if the patient presents any signs of discomfort. Also if the subject requests, the intensity can be reduced up to 50% of HR max or the duration can be reduced up to 15min. To evaluate the adverse effects of AE during the training, we will record any musculoskeletal symptoms, such as pain, fatigue, tingling or cardiovascular symptoms, such as shortness of breath [29]. As recommended by the ACSM guidelines for AE in patients with FM, we will monitor the level of pain and fatigue continuously throughout the tests using the VAS. We will also follow the emergency procedure guidelines from the ACSM.

If a subject is not comfortable to perform one of the described assessments, we will make a note in the study binder and proceed to the next one.

VIII. BIOSTATISTICAL ANALYSIS

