The primary analysis: All the analyses will be performed as intention-to-treat in which all subjects undergoing randomization who receive at least one intervention session (randomization will take place immediately before the first intervention) will be included. We will conduct sensitivity analyses and test different models of handling missing data (LOFC and MI). The change in the primary efficacy endpoint, CPM (and also TSPS), from baseline to week 4 will be tested with a mixed linear model. This model will be adjusted for important demographic variables (i.e., gender) and also baseline clinical parameters where appropriate. All tests will be two-sided (alpha level, 0.05). We will initially test our main hypothesis that the combined treatment induces a greater increase in CPM (and decrease in TSPS) as compared to the control condition. If the effect is significant, we will then test differences between the combined group vs these two interventions alone.

[figure not shown]
In order to understand the time effect of this intervention (using the secondary endpoints added in this model (week1 and follow-up)), we will run a secondary mixed linear model to estimate the rate of change over time by also including an interaction between treatment and time as to detect whether treatment effect changes differently according time. If the interaction is not significant we will then test whether there is a main effect of time that is independent of treatment level (interaction will be then removed from the model). We will adjust this model for important covariates such as age, gender, pain levels (numeric pain scale – NPS), and other baseline clinical outcomes where appropriate. For the secondary clinical variables with a significant effect we will also test whether they moderate the interventions' effects on our mechanistic outcomes, thereby gaining additional mechanistic insights.

To complete our analysis, we will apply a path analysis [1, 2] to the outcome data (CPM and TSPS) to determine if endogenous pain modulation changes (as indexed by CPM and TSPS) associated with the combined intervention (tDCS and AE) is related to direct effects versus indirect effects through improvements in secondary outcomes. We propose that a direct effect of tDCS and AE on the endogenous pain inhibitory system can be inferred if the treatment effect cannot be explained by changes in psychological or functional outcomes.

[figure not shown]

[figure not shown]
Detailed Protocol 23

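### The skip rule covers the primary CPM and TSPS tests, and completing them at baseline is not a condition of randomisation, so a subject can be randomised and treated without the baseline that the primary change endpoint needs

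*Combined protocol and SAP*

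**What the plan says.** Section VII (Description of Assessments) sets out TSPS and CPM first, then TMS, EEG, questionnaires and adverse-effect forms. Its closing rule applies to all of them: "If a subject is not comfortable to perform one of the described assessments, we will make a note in the study binder", after which staff go on to the next item. CPM and TSPS are not exempted, and nothing is said about a repeat attempt or about classifying the reason.

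Both primary tests are meant to be painful. For TSPS, "they will receive 1 train of 15 repetitive heat stimuli at 0.4 Hz to the same area". For CPM, heat at the subject's pain-60 temperature is held for 30 s, and the opposite hand "will be immersed in a bath of water set at 10 to 12°C for 30 seconds" before the heat is repeated with the hand still in the water.

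On entry to randomisation, the Visit 1 text says: "If he/she complete the pre-training walking successfully as described above, then he/she will be randomized during visit 1.1". The Visits 1.1 – 1.3 paragraph says "Subjects will be randomized during visit 1.1" and lists baseline CPM and TSPS for the same visit, adding that "we will offer the possibility of splitting this visit into two visits if the subject gets too tired". The order of testing and randomisation within the visit is not given. The sensory inclusion criterion in section IV concerns only Von-Frey sensation on the forearm.

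Section VIII (Planned Analysis) defines the primary analysis as "The change in the primary efficacy endpoint, CPM (and also TSPS), from baseline to week 4", tested with a mixed linear model. The intention-to-treat set is everyone randomised who has at least one intervention session; a baseline measurement is not required. Last observation carried forward and multiple imputation are named as sensitivity analyses.

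**The concern.** Each rule is reasonable alone; the difficulty is their combination. A subject may decline CPM or TSPS at visit 1.1, be randomised on the strength of eligibility and the walking test, go through the 16 stimulation sessions, and belong to the primary analysis set without a change score. No rule says how a missing baseline CPM or TSPS is handled.

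Two things are at stake, and they should be kept apart. A baseline declined before allocation is known cannot depend on the arm, so it costs evaluable subjects and some generalisability. A test declined after randomisation, above all at the end-of-treatment visit (visit 17), could differ by arm and so could bias the comparison. Because the reason for a refusal is only noted in a binder, the planned missing-data analyses would have no coded reason to work with.

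**Working it through.** **1. What permits the situation**

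- Skip rule: all assessments in section VII, no exception for the primary ones.
- Condition for randomisation: eligibility plus the pre-training walk. Completed CPM and TSPS are not mentioned.
- Analysis set: randomised plus one session.
- Endpoint: change from baseline. The concomitant-medication item in section VII identifies visit 1.1 as the baseline visit.

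**2. Whether later measurements can stand in**

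CPM and TSPS are repeated at visits 1.3 and 2. By then the subject is randomised and has been through conditioning exercise that is aerobic in some arms and non-aerobic in others. The main comparison, combined treatment against control, is between arms that differ in that exercise. A visit 1.3 or visit 2 value may therefore already contain part of the treatment effect. Last observation carried forward cannot fill a missing baseline, because nothing precedes it. Multiple imputation could, under its own assumptions.

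**3. Reproducing the plan's sample size**

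Inputs from section VIII: standardised effect 0.90, two-sided alpha 0.05, power 85%, dropout 20%, four equal arms.

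- Normal approximation: n = 2 × (1.960 + 1.036)² / 0.90² = 22.2, so 23 per arm.
- Dropout: 23 / 0.80 = 28.75, so 29 per arm and 4 × 29 = 116. This matches the plan.
- A t-test calculation gives 23.17, so 24 per arm. The plan's 29 then follows from 24 × 1.20 = 28.8, whereas 24 / 0.80 = 30 would give 120.

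Expected evaluable per arm: 29 × 0.80 = 23.2, with t-test power 85.0%. There is no spare margin.

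**4. Power if primary tests are also skipped**

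The documents give no skip rate. The rates s below are assumptions, applied on top of the 20% dropout. Evaluable per arm = 29 × 0.80 × (1 − s). The last column is 4 × 23 / (0.80 × (1 − s)), rounded up within each arm.

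| Assumed s | Evaluable per arm | t-test power | Total N to keep 23 evaluable per arm |
|---|---|---|---|
| 0% | 23.2 | 85.0% | 116 |
| 5% | 22.04 | 83.1% | 124 |
| 10% | 20.88 | 81.0% | 128 |
| 15% | 19.72 | 78.6% | 136 |
| 20% | 18.56 | 76.0% | 144 |

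**5. Upper bound on bias from skipping after randomisation**

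Suppose the missing subjects are exactly the worst fraction p of one arm on a normal score, and nobody is missing from the other arm. That arm's observed mean then shifts by φ(z_p) / (1 − p):

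- p = 5%: 0.1031 / 0.95 = 0.109 SD
- p = 10%: 0.1755 / 0.90 = 0.195 SD

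This takes refusal and outcome to be perfectly correlated. Under joint normality the shift scales with the correlation; at an assumed 0.3 it is 0.3 × 0.109 = 0.03 to 0.3 × 0.195 = 0.06 SD. The sign depends on the arm: losing the worst scorers from control makes control look better and shrinks the difference, while losing them from the combined arm enlarges it.

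**The case against.** Section VIII places randomisation directly ahead of the first intervention. The natural reading is that the tests come first, then allocation, then the first conditioning session. That stands as evidence of intent. It does not require the tests to be completed, and it does not say which part of a split visit holds randomisation. Schedule figures are missing from the available text, so a requirement stated only there cannot be excluded.

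A reader might infer that the most pain-sensitive subjects are the ones lost. The documents do not support this. Heat is set individually, and if 43 °C is too painful "we will stop the series and will provide additional stimuli at lower temperatures of 41 and 42" °C, so a sensitive subject receives a lower temperature aimed at the same rating. TSPS uses that same temperature. Only the cold bath is fixed, and it belongs to CPM alone, although no rule covers a subject for whom 41 °C is still too painful. CPM and TSPS are also within-subject difference scores, and nothing in the plan links declining a test to a poor change in either.

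It is also fair to say that silence on a repeat attempt is not a prohibition, that the data at visits 1.3 and 2 are imperfect rather than absent, and that the scope of the 20% dropout figure is undefined, so some skipping may already be inside it. Those points limit the size of the problem. They do not supply the missing condition.

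**Conclusion.** The point holds as a cheap improvement to the design. As written, the plan allows a subject to be randomised, treated and included in the intention-to-treat set without the baseline CPM or TSPS that the primary endpoint needs, and the later repeats are not clean replacements.

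The expected cost is modest: about 2 percentage points of power at an assumed 5% skip rate and about 4 at 10%, starting from 85.0%. This rests on the plan's effect of 0.90, on skips being additional to the 20% dropout, and on a subject without a baseline contributing nothing to the primary comparison.

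Two stronger readings go too far. One is that baseline is taken after the arm is known: a split visit leaves this open, but the placing of randomisation in section VIII makes it not the likeliest reading. The other is that the primary result would be biased by 0.11 to 0.20 SD: that range is an upper-bound illustration, with perfect correlation, losses in one arm only and assumed rates. Bias is possible only if skipping after randomisation differs by arm and is related to outcome. Its size and direction are unknown, and if the losses fell on the worst-scoring controls it would run towards the null.

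**What to change.** 1. In the visit 1.1 text, require completed baseline CPM and TSPS before the randomisation envelope is opened. If the visit is split, randomise only in the second part, after these tests. A subject who cannot complete them is not randomised.
2. Exempt CPM and TSPS from the simple binder-note rule. Keep the right to refuse, offer one repeat (before the next treatment session, or within a few days for visit 17), and record the reason in coded form for the missing-data sensitivity analysis.

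The first change protects the baseline. The second addresses skipping after randomisation, which the first cannot reach; some missing values will remain because refusal stays allowed.

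The cost is wording in the visit sequence and the worksheet. A few subjects will stop before randomisation, and the population becomes those able to complete the tests, which suits a mechanistic endpoint. The sample size stays at 116.

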In addition, the exercise level we are using here is exactly the same we used in our previous study (*Mendonca ME, Simis M, Grecco LC, Battistella LR, Baptista AF, Fregni F. Transcranial Direct Current Stimulation Combined with Aerobic Exercise to Optimize Analgesic Responses in Fibromyalgia: A Randomized Placebo-Controlled Clinical Trial. Front Hum Neurosci. 2016 Mar 10;10:68*). We have found this to be an effective and also reasonable level of exercise for FM patients.

Finally all subjects will participate in a 1-week exercise conditioning program according to their randomized group as explained below.

Aerobic Exercise: Each session of moderate intensity AE will last 30 minutes (brisk walking). FM patients will be walking on a treadmill with a workload intensity set to a maximum of 60-70% of age predicted maximal heart rate, following the formula $HR_{max} = 208 - (0.7 * \text{age})$ [36]. Before and after each AE session, there will be warm-up and cool down periods (explained below). During the AE session, the intensity will be modulated based on patient's HR_{max} .

Non-aerobic Exercise: The non-aerobic (nAE) exercise will have a 30 min-duration, but the workload intensity will be set within 5-10% baseline heart rate. We also used this method in our preliminary study [29]. The warm-up and cool down periods will consist of 3-minutes walking on the treadmill at a comfortable self-selected speed.

Conditioning exercise program:

The two groups will participate in a different conditioning exercise program according to their group assignment. Stimulation will only start after the conditioning exercise program.

[figure not shown]
Group of Aerobic exercise: in this group participants will exercise (brisk walking in the treadmill – 60-70% of HRmax) following the schedule below (3 sessions within 1 week):

[figure not shown]
- Week 1: up to 15 min on the Monday (minimum 10 min), up to 25 min on Wednesday and up to 30 min on Friday (days of the week can change to adjust to subject schedule)

If a subject from this group cannot progress beyond 20 min at 60-70% HR max over the initial 1-week period, they will be excluded from further involvement in the study. If they reach 20 min at 60-70% of their HR max, he/she can progress to 30min during the second phase and this will be noted.

Group of Non-aerobic exercise: in this group participants will walk at within 5-10% of their baseline heart rate following the schedule below (3 sessions within 1 week):

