Sample Size Calculation: This study's original sample size calculation was based on an expected effect size of 0.78, with 85% statistical power and a significance level of 0.05. However, after 6 years of the original sample size calculation (it was done in 2017 upon grant submission, see appendix 2), we have observed in our recent study in collaboration with other colleagues and recent meta-analyses effect sizes ranging from 0.9 to 1.26, which are larger than we initially anticipated. Considering this new information, we re-estimated the sample size to ensure we do not expose subjects to the burden of participating in a study that involves a placebo arm. Also, this would make the study feasible to be completed in the 5-year period of this grant, given our recruitment was significantly affected by the COVID pandemic, especially in the years 2020 and 2021. We have recalculated the sample size using the smallest reported effect size (0.90) using the t-test calculation for the difference between two independent means (to test for the main hypothesis) – this is the same method used in the original sample size calculation; and determined that we need a total of 116 participants (29 in each group) to achieve 85% power (as planned before). We assumed a type I error of 5% (alpha), and a type 2 error of 15% (beta). We also made this calculation considering the same parameters used in the original sample size calculation, such as dropout rates of 20%. The sensitivity analysis for the sample size calculation is summarized in the table below.

[figure not shown]
Therefore, we reduced the sample size from 148 to 116 participants, which will maintain the same planned statistical power (85%). This revised sample size will allow us to detect the more precise effect sizes currently reported in the literature and will also make the study feasible to be completed on time, given the large impact of the COVID pandemic on our study.

[figure not shown]
Planned Analysis:

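### LOCF and MI together are not a principled check for informative dropout; replace LOCF with delta-adjusted MI and say whether participants removed during conditioning are analysed

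*Combined protocol and SAP*

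**What the plan says.** All references are to the combined protocol and SAP.

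- **Primary analysis (section VIII, Planned Analysis).** The change in CPM, and also TSPS, "from baseline to week 4 will be tested with a mixed linear model". The analysis set is "all subjects undergoing randomization who receive at least one intervention session", and randomisation is said to come directly before the first intervention.
- **Missing data (same paragraph).** "We will conduct sensitivity analyses and test different models of handling missing data (LOFC and MI". The readable text does not give the MI model, the visit that LOCF carries forward, or the assumption behind either method. It contains no delta-adjusted, reference-based, pattern-mixture or tipping-point analysis.
- **Expected loss (section VIII, Sample Size Calculation).** The plan uses "dropout rates of 20" per cent, with no split by arm.
- **Conditioning exercise program.** Aerobic-group participants who do not get past the stated exercise duration in the conditioning week are removed: "they will be excluded from further involvement in the study". No matching rule is stated for the non-aerobic group. Stimulation starts only after conditioning.
- **Visit description.** Randomisation is at visit 1.1, before conditioning. CPM and TSPS are measured at visits 1.1, 1.3, 2, 6, 11, 14, 17 and 18. Follow-up is encouraged even for participants who miss more than 20% of sessions.

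**The concern.** A missing-data sensitivity analysis should show how far the primary conclusion depends on an assumption that the data cannot verify. A likelihood-based mixed model and standard MI both assume that, given what was observed, the missing week-4 values behave like the observed ones. If they agree, that says little about dropout related to the unseen outcome.

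LOCF does leave that assumption, but in one fixed way: a participant who drops out is taken to have stopped changing. That is hard to defend when the endpoint is change over four weeks. If LOCF disagrees with the primary result, the reader cannot tell informative dropout from LOCF's own bias. If it agrees, that may be chance, because its bias can go either way.

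The question matters more than usual here. Removal for poor exercise tolerance after randomisation is stated for the aerobic groups only, so in the lead contrast (combined versus control) it can affect one side only. Such removal could plausibly relate to pain modulation. What is at stake is the robustness statement attached to the primary result.

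**Working it through.** **Inputs from the plan.** Effect size d = 0.90, power 85%, two-sided alpha 0.05, dropout 20%, 29 per group (section VIII).

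**Inputs that are assumptions.** Visit SD 1 and correlation 0.5 between visits, so the SD of change is √(2 × (1 − 0.5)) = 1. Half of dropouts leave before any post-baseline value and carry none of the change. The other half carry a mid-treatment value with half the change. The average share carried is then f = 0.5 × 0 + 0.5 × 0.5 = 0.25. The improvement c common to both arms and any unequal dropout are also assumptions.

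**1. The plan's own figure.** The plan describes the calculation as "using the smallest reported effect size (0.90) using the t-test calculation for the difference between two independent means". By the normal approximation, n = 2 × ((1.960 + 1.036)/0.90)² = 22.17, so 23 per group. Then 23/0.80 = 28.75, so 29 per group and 4 × 29 = 116, as stated.

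**2. Expected LOCF effect.** With dropout p₁ in the combined arm and p₀ in control,

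LOCF effect = (c + d) × (1 − p₁ + f p₁) − c × (1 − p₀ + f p₀).

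| Dropout, combined / control | c (SD) | Calculation | LOCF effect |
|---|---|---|---|
| 20% / 20% | any | 0.90 × 0.85 | 0.765 |
| 30% / 10% | 0.8 | 1.7 × 0.775 − 0.8 × 0.925 | 0.58 |
| 30% / 10% | 0 | 0.90 × 0.775 | 0.70 |
| 10% / 30% | 0.8 | 1.7 × 0.925 − 0.8 × 0.775 | 0.95 |
| 10% / 30% | 0 | 0.90 × 0.925 | 0.83 |

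Simulation with 29 per arm agrees: about 0.76 at 20%/20%; 0.58 with 95% interval coverage of 79% at 30%/10% and c = 0.8; and 0.95 for the reverse split.

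**3. Dependence on timing.** At 20% in both arms the effect is 0.90 × (0.80 + 0.20 f). This is 0.72 at f = 0, 0.81 at f = 0.5 and 0.855 at f = 0.75.

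**4. No true effect.** At 30%/10% and c = 0.8, LOCF gives 0.8 × 0.775 − 0.8 × 0.925 = −0.12. The simulated two-sided rejection rate is about 7.5%, nearly all of it against the combined arm. With c = 0 the false difference disappears and rejection returns to about 5%.

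**5. What a delta adjustment would show.** Suppose combined-arm dropouts do worse than missing at random predicts by δ. The effect is then 0.90 − 0.20 δ: 0.85 at δ = 0.25 SD, 0.80 at 0.5, 0.70 at 1.0 and 0.60 at 1.5. Holding the standard error at that of 23 completers per arm (a simplification), the critical difference is 2.015 × √(2/23) = 0.594, and the tipping shift is (observed effect − 0.594)/0.20:

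- observed effect 0.90: (0.90 − 0.594)/0.20 ≈ 1.5 SD
- observed effect 0.65: (0.65 − 0.594)/0.20 ≈ 0.3 SD

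The first result would be robust and the second fragile. Neither LOCF nor missing-at-random MI would separate them.

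**The case against.** **LOCF is only a sensitivity analysis.** This stands. A reader might infer that the LOCF figures above are biases in the trial's main result. They are not, because the mixed model provides that test.

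**It is too much to say that nothing departs from missing at random.** This also stands. LOCF is itself such a departure, though a single crude one, and the MI model is unspecified.

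**MI may add something.** The plan places the week-1 and follow-up data in a separate secondary mixed model, so the primary model may use only the week-4 change. MI that includes the intermediate CPM and TSPS values would then condition on more information and make missing at random more plausible. That is a reason to write the MI model down. It would still not test the assumption.

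**Arm-specific loss may never reach these analyses.** A reader might infer that the conditioning rule makes LOCF carry near-baseline values forward mainly in the aerobic arms. That holds only if a conditioning session counts as an intervention session. If intervention means the stimulation phase, those removed earlier fall outside the analysis set, and neither LOCF nor delta-adjusted MI reaches them. The passages leave this open.

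**The size rests on assumptions, and loss may be small.** The plan gives one dropout rate, no split by arm and no count of removals, and it encourages continued follow-up. The simulated dropout is also at random given arm, so it describes LOCF and not how the mixed model or MI would behave under informative dropout. All of this is correct.

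**The plan may say more elsewhere.** Figures and later pages are not shown, so the absence is established only for the readable text.

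**Conclusion.** The point holds as an inexpensive improvement to a stated method. The readable plan offers two checks: standard MI, which shares the mixed model's missing-at-random assumption, and LOCF, which replaces it with one implausible alternative. Together they are not a principled examination of informative dropout.

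In the illustrations, a true 0.90 becomes anything from 0.58 to 0.95 under LOCF, depending on dropout by arm, its timing and the common improvement. Only the 0.90, the 29 per arm and the 20% come from the plan. At that 20% in both arms, the attenuation is 5% to 20% for f between 0.75 and 0. The lesson is that the bias cannot be predicted in size or sign, which makes LOCF uninformative as a check.

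The documents do not support a claim that the primary estimate is biased, that LOCF would favour treatment, or that the false-positive rate is generally inflated. The 7.5% in step 4 needs both unequal dropout and a sizeable common improvement, and in that case it works against the combined arm.

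**What to change.** 1. Delete LOCF. Keep MI under missing at random as the base sensitivity analysis, and specify its model, including arm, baseline covariates and the intermediate CPM and TSPS values.
2. Add delta-adjusted MI. Shift the imputed week-4 CPM and TSPS of dropouts in the active arms towards less benefit, in prespecified steps, and report the shift at which the conclusion changes.
3. Add one control-based scenario, in which missing week-4 values in the active arms are imputed from the control-arm model.
4. Report dropout by arm, timing and reason.
5. State whether participants removed during conditioning, after randomisation at visit 1.1, are in the analysis set. Reconcile the conditioning program, the visit description and the definition of the analysis population on this. The sensitivity analysis covers these participants only if they are in the set; in either case, report their number by arm.

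The cost is a short SAP edit and a little programming. The sample size, visits and primary model do not change. The real downside is that the resulting robustness statement may be less favourable.
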